#### **6.4.3 Cycles 7-12, Day 1 (~10-15 months post-BMT)**

- Physical examination and vital signs (including weight)
- ECOG performance status
- CBC and clinical chemistry panel
- Screening for viruses (see Section 6.5.6)
- Blood sample collection and bone marrow aspirate for MRD analysis
- CT/MRI/PET scans (12 months post-BMT)
- Treatment with acalabrutinib 129 mg PO BID
- Concomitant medication review and AE monitoring

#### **6.4.4 Cycle 13 and Beyond, Day 1 ( $\geq 16$ months post-BMT)**

- Physical examination and vital signs (including weight)
- ECOG performance status
- CBC and clinical chemistry panel
- Screening for viruses (see Section 6.5.6)
- Blood sample collection for MRD analysis

- CT/MRI/PET scans (18 and 24 months post-BMT)
- Treatment with acalabrutinib 129 mg PO BID
- Concomitant medication review and AE monitoring

#### **6.4.5 End of Treatment/Early Termination Visit**

Please refer to Section 3.4 for the reasons for study drug discontinuation/early termination. If either the study drug or observations are discontinued, the reason will be recorded in the electronic case report form (eCRF) and source document. Patients who complete or discontinue the study drug should have the following evaluations performed as soon as possible.

- Screening for viruses (see Section 6.5.6)
- Fresh lymphoma biopsy (at PD)
- Concomitant medication review and AE monitoring

Patients prematurely discontinuing from the study drug must be followed for AEs and concomitant medication use for 30 days following the last administration of study drug or until resolution/stabilization of any ongoing AEs attributed to the medication.

Patients who discontinue from the study drug may be treated with other therapies at the discretion of the Investigator.

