|-----------------------------|--|

|                                 |   |
|---------------------------------|---|
|                                 | 
17. Breastfeeding or pregnant.
 
18. Concurrent participation in another therapeutic clinical trial.
 
19. Psychological, familial, sociological, or geographical conditions that do not permit compliance with the protocol.
 
20. The inability to swallow tablets.
   |
| Statistical Methodology: | 
The primary endpoint is the percentage of subjects who are alive and free of disease progression or relapse at 2-years post-BMT. A sample size of 45 subjects produces a two-sided 95% confidence interval of 65%-95% when the observed percentage is 80%. To account for a 10% non-evaluable rate, the total sample size will be 50 patients.
 |

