#### **6.4.6 Long-Term Follow-up/End of study**

At 2 years post-BMT, a follow-up visit will be performed for all MRD and MRD+ subjects every 3 months until the time of PD, death, withdrawal of consent, start of another anticancer therapy, the study is terminated, or the 5-year post-BMT time point is reached. The following procedures and tests will be done at each follow-up visit:

- Fresh lymphoma biopsy (at PD)
- PFS status

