## **9. RESPONSE EVALUATIONS AND MEASUREMENTS**

### **9.1 Progression-free Survival**

Progression-free survival is defined as the time from Day 0 of BMT until the date of objective radiological PD according to RECIL or death (by any cause in the absence of PD). Patients who are alive and free from PD will be censored at the date of last tumor assessment. Patients who begin subsequent therapy prior to PD or death will be censored at the date of last tumor assessment prior to the start of subsequent therapy.

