### **10.2 Sample Size Considerations**

The primary endpoint is the percentage of patients who are alive and free of PD or relapse at 2 years post-BMT. A sample size of 45 patients produces a two-sided 95% CI of 65%-90% when the observed percentage is 80%. To account for a 10% non-evaluable rate, the total sample size will be 50 patients.

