#### **10.4.2 Efficacy Analysis**

All efficacy analyses will be performed using the Efficacy Analysis Set.

- PFS is defined as the time from Day 0 of BMT to objective radiological PD or death on study. PFS will be evaluated as Kaplan-Meier estimates of the percentage of subjects who receive at least one dose of study drug and who are alive and free of PD or relapse at 2 years post-BMT according to RECIL (Younes et al 2017). Data for subjects who are still alive and free from progression at the time of data cut-off date, are lost to follow-up, have discontinued the study, or have initiated a subsequent protocol therapy will be censored on last assessment (or, if no post-baseline tumor assessment, at the time of first dose plus 1 day). Approximate 95% CI for median duration of PFS will be computed using the formula proposed by Brookmeyer and Crowley.
- Minimal residual disease status will be examined by NGS on all bone marrow aspirate and blood samples collected up to 2 years post-BMT to determine the conversion rate from MRD+ to MRD while taking acalabrutinib, correlate MRD status with PFS, and identify mutations that correlate with disease relapse. An MRD status will be defined as all results from whole blood and BM that are negative for the presence of residual clonal cells (with assay sensitivity of 10^-6). An MRD+ status will be defined as all results from whole blood or BM that are positive for residual clonal cells per Adaptive Biotechnologies' reporting methods.

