- n. Patients with a known history of hepatitis C virus (HCV) or who are hepatitis C antibody positive should be tested for HCV RNA during screening. No further testing beyond screening is necessary if PCR results are negative, except if clinically indicated (see Section 6.5.6).
- o. If not obtained during Screening #1 (prior to BMT)
- p. Collect a fresh lymphoma biopsy at disease progression
- q. **MRD analysis with blood sample:** Collect a blood sample prior to beginning maintenance on Day +100 (Screening #2), 6 months (~Cycle 4 Day 1), 1 year (~Cycle 10 Day 1) and 2 years post-BMT (~Cycle 22 Day 1).
- r. **MRD analysis with bone marrow biopsy and aspirate:** Collect a bone marrow biopsy and aspirate prior to beginning maintenance on Day +100 (Screening #2) and at 1 year post-BMT (~Cycle 10 Day 1).
- s. CT/MRI/FDG-PET scans will be done post-BMT (Day 80-100), at 6 months, 12 months, 18 months and 24 months. Thereafter, scans will be done per institutional standard operating procedures.
- t. Record all AEs regardless of seriousness or relationship spanning from the first dose of acalabrutinib until 30 calendar days after discontinuation or completion of study drug.
- u. Coagulation testing will include PT/INR or aPTT.

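### The protocol conflicts with itself on whether scans and PFS contact continue between an early drug stop and 2 years post-BMT, which leaves the 2-year PFS estimate exposed

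*Combined protocol and SAP*

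**What the plan says.** **Passages that suggest assessment lapses after an early stop**
- Section 6.4.5: "Patients who complete or discontinue the study drug should have the following evaluations performed as soon as possible". The list covers virus screening, a biopsy at progression, medications and adverse events. The Appendix D imaging row is likewise blank under the end-of-treatment and follow-up columns.
- Sections 6.4.2 to 6.4.4 list the scans within treatment-cycle visits that also list dosing. The Planned Clinic Visits table ties them to Cycles 4, 10, 16 and 22.
- Section 6.4.6: "At 2 years post-BMT, a follow-up visit will be performed for all" MRD-negative and MRD-positive subjects, then every 3 months. PFS status is listed here and not in Section 6.4.5.

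**Passages that suggest it continues**
- Appendix D footnote s: "CT/MRI/FDG-PET scans will be done post-BMT (Day 80-100), at 6 months, 12 months, 18 months and 24 months". It sets no on-drug condition.
- Footnote h allows a 3-monthly telephone call for PFS in the follow-up column and gives no 2-year start.
- Footnote f runs the last visit column to 5 years post-BMT, well past the end of dosing.
- Section 6.4 dates visits and assessments from the transplant. Section 5 has all subjects followed for PFS for up to 5 years.

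**How the data are used**
- Section 10.4.2: "PFS will be evaluated as Kaplan-Meier estimates of the percentage of subjects who receive at least one dose of study drug" who are alive and progression-free at 2 years post-BMT.
- Section 9.1: "Patients who are alive and free from PD will be censored at the date of last tumor assessment". Progression must be objective and radiological.
- Section 10.3 requires an adequate post-baseline assessment for the Efficacy Analysis Set, unless the patient discontinued for death or progression first.

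**The concern.** The primary endpoint depends on scans up to 24 months after transplant. A site that works from the body text could reasonably stop imaging when the drug stops. On that reading, a patient who stops at month 8 was last scanned at month 6, has no further disease assessment until month 24 (16 months after stopping), and is censored at month 6 unless a later scan is obtained. A telephone call does not change this, because the censoring date is that of the last tumor assessment.

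Kaplan-Meier treats a censored patient as having the same later risk as those still followed. If patients who stop maintenance have a higher risk afterwards, the estimate moves toward PFS while on drug and overstates PFS in all treated patients. If their risk is the same, precision is still lost.

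A patient who stops before the 6-month scan without progression or death may drop out of the Efficacy Analysis Set altogether under Section 10.3, although Section 10.4.2 has a rule that censors patients without a post-baseline scan at first dose plus 1 day.

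About 10 sites are planned, so different sites could apply the text differently. Scans that were not done cannot be recovered at analysis.

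**Working it through.** **1. The plan's own precision.** Section 10.2: "A sample size of 45 patients produces a two-sided 95% CI of 65%-90% when the observed percentage is 80"%. The exact (Clopper-Pearson) interval for 36/45 is 65.4% to 90.4%, which agrees. "To account for a 10% non-evaluable rate, the total sample size will be 50 patients": 45/(1 − 0.10) = 50, which agrees. (The synopsis gives an upper limit of 95% for the same case. None of the exact, Wilson, Wald or log-log intervals reproduces it. That is a separate item to reconcile.)

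**2. What the text settles after an early stop**

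| Question | Body text | Appendix D and general statements |
|---|---|---|
| Scan at end of treatment? | None (6.4.5) | None (imaging row) |
| Later scans to month 24? | Only within cycles (6.4.2–6.4.4) | Calendar months, no drug condition (footnote s; 6.4) |
| PFS contact before year 2? | Starts at year 2 (6.4.6) | Every 3 months, no start given (footnote h); all subjects followed (Section 5) |

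Only the first row is consistent.

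**3. Size if the body text is followed.** Assumptions, none of them from the documents except the Day 100 start, the scan times and the 80% planning figure:
- Start at Day 100 = 100/30.44 = 3.29 months. On-drug PFS from there to month 24 is 80%, so the hazard is −ln(0.80)/(24 − 3.29) = 0.0108 per month.
- A share d stops drug, at times uniform from Day 100 to month 24. After stopping, the hazard is multiplied by HR.
- Events up to the stop are counted. Other stoppers are censored at their last scan (Day 100, or month 6, 12 or 18).

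Large-sample simulation, in percent; bias = Kaplan-Meier − true:

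| d | HR | True 2-year PFS | Kaplan-Meier | Bias (points) |
|---|---|---|---|---|
| 10% | 1 | 80.0 | 79.7 | −0.3 |
| 10% | 2 | 79.2 | 79.8 | +0.5 to +0.6 |
| 10% | 3 | 78.5 | 79.8 | +1.3 |
| 30% | 1 | 80.0 | 79.1 | −0.9 |
| 30% | 2 | 77.5 | 79.1 | +1.6 |
| 30% | 3 | 75.3 | 79.1 | +3.8 |

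(Biases are from unrounded values and vary by about 0.1 between runs.) At 20% stopping the biases for HR 2 and 3 are +1.1 and +2.5. The small negative values at HR 1 arise because the model counts events up to the stop but discards event-free time between the last scan and the stop.

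**4. A second parameterisation.** Here the true overall rate is fixed at 80%, and progression is detected only at scans, so progression between the last scan and the stop is also missed. The bias at 10% stopping is 0.0, +0.8, +1.5 and +2.5 points for HR 1, 2, 3 and 5. At 30% it is +0.1, +2.2, +3.9 and +6.4. If stoppers keep the four scheduled scans, the bias is nil.

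**5. Precision.** With 45 patients and full follow-up, 45 × 0.80 = 36 are at risk at 24 months, and SE = √(0.8 × 0.2/45) = 6.0 points. With 30% stopping, 45 × 0.70 × 0.80 = 25.2, so about 25 remain, and the simulated SE is 6.8 points.

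**6. Bounds without a hazard assumption.** If 5 of 45 have unknown 2-year status and 32 of the other 40 are event-free, the rate lies between 32/45 = 71% and 37/45 = 82%. With 9 unknown and 29 of 36 event-free, it lies between 29/45 = 64% and 38/45 = 84%.

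**The case against.** A reader might infer that the protocol definitely provides no imaging and no PFS contact from an early stop until 2 years, and so definitely loses these patients informatively. The documents do not support that.

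- Footnote s sets calendar scan times without an on-drug condition, and goes on to say what happens to scans after 24 months, when dosing has ended.
- The last maintenance column extends to 5 years, so sitting in that column does not mean on drug.
- Footnote h and Section 5 can be read as PFS contact for everyone after the end-of-treatment visit.
- Section 6.4.5 itself separates stopping the drug from stopping observations.
- Stopping drug is not a censoring reason in Section 9.1 or 10.4.2. Progression and death remain events whenever they are captured, and the model above leaves out all events after the stop, including deaths that might still be recorded.

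A reader might also take the 30% in Section 3.5 as the expected rate of stopping for adverse events. It is the level at which enrollment stops for a safety review, not a forecast, and serves here only as the upper end of an assumed range.

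On size, the largest bias in the main model (+3.8 points) is below one standard error (6.0 to 6.8 points), in a single-arm study whose sample size rests on interval width.

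All of this stands, and it limits the point to a conflict in the text. It does not remove the conflict: no passage says outright that scans or PFS contact continue after an early stop, and the sections a site would consult on drug discontinuation point the other way.

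**Conclusion.** The point holds as a conflict between Sections 6.4.2 to 6.4.6 and the Planned Clinic Visits table on one side, and Section 5, Section 6.4 and Appendix D footnotes f, h and s on the other. It is worth correcting because it governs the collection of primary-endpoint data.

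The consequence is conditional. It arises only if sites follow the body text, and upward bias arises only if risk rises after stopping. For 10% to 30% stopping and hazard ratios of 2 to 3, with 80% on-drug PFS, the main model gives roughly half a point to four points upward. With no change in risk there is little or no bias, but fewer patients are at risk at 24 months. The stopping share, the hazard ratio and the uniform stop times are assumptions, so the figures show scale and do not predict this trial's result.

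Censoring at the start of new therapy (Section 9.1) is a separate possible source of informative censoring, and resolving this conflict would not remove it.

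**What to change.** Reconcile Sections 6.4.5 and 6.4.6 with Appendix D by stating two things:

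1. The scans already scheduled at 6, 12, 18 and 24 months are timed from BMT and continue for all treated patients, whatever their drug status, until progression, death, new anticancer therapy or withdrawal of consent.
2. The 3-monthly PFS contact, by telephone if preferred as footnote h allows, starts at end of treatment and not at 2 years.

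The first statement matters more, since calls alone do not move the censoring date. It would also largely avoid losing patients who stop before the 6-month scan from the Efficacy Analysis Set.

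The cost is protocol wording and a few extra telephone contacts for early stoppers, with no scan beyond footnote s. If the sponsor already intends this, the change only records it.

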#### **6.4.6 Long-Term Follow-up/End of study**

At 2 years post-BMT, a follow-up visit will be performed for all MRD and MRD+ subjects every 3 months until the time of PD, death, withdrawal of consent, start of another anticancer therapy, the study is terminated, or the 5-year post-BMT time point is reached. The following procedures and tests will be done at each follow-up visit:

- Fresh lymphoma biopsy (at PD)
- PFS status

### **6.5 Study Assessments**

#### **6.5.1 Medical History and Demographics**

A complete medical history will be taken. Information to be documented includes demographics, prior medical illnesses and conditions, prior surgical procedures, date and stage of original diagnosis and details of prior chemotherapy/radiotherapy administered and other treatments for cancer (including type of drugs, dosages, schedule or administration, response and response duration) and Mantle Cell Lymphoma International Prognostic Index (MIPI).

Concurrent medical signs and symptoms must be documented to establish baseline severities.

#### **6.5.2 Physical Examinations (Including Performance Scale and Vital Signs)**

A complete physical examination will be done at baseline, at each visit, at the end-of-treatment visit, and long-term follow-up visit as well as at the discretion of the Investigator. Examinations will include documentation of height (at screening only), weight, vital signs, and ECOG

performance status (Appendix A). Any abnormal or clinically significant findings from the physical examination must be recorded on the appropriate eCRF page.

### **6.5.3 12-Lead Electrocardiogram**

ECGs will be done according to Appendix D and at the discretion of the Investigator. Each will be performed with the patient in a supine position having rested in this position for at least 10 minutes before the reading.

### **6.5.4 Pregnancy Testing**

In WoCBP, a serum beta human chorionic gonadotropin or urine pregnancy test must be performed at the time of screening and 72 hours prior to the start of treatment.

### **6.5.5 Laboratory Assessments**

Laboratory samples (CBC, clinical chemistry, urinalysis, and virology) are to be collected as outlined in Appendix D. Laboratory results will be graded using NCI CTCAE Version 5.0.

Hematology studies must include CBC with differential including, but not limited to, white blood cell count, hemoglobin, hematocrit, platelet count, ANC, and absolute lymphocyte count.

Coagulation testing will include PT/INR or aPTT.

Serum chemistry will include albumin, alkaline phosphatase, ALT, AST, bicarbonate, blood urea nitrogen (BUN), calcium, chloride, creatinine, glucose, lactate dehydrogenase (LDH), magnesium, phosphate/phosphorus, potassium, sodium, total bilirubin, total protein, and uric acid.

If an unscheduled ECG is done at any time, then an electrolyte panel (e.g., calcium, magnesium, and potassium) must be done to coincide with the ECG testing.

A urinalysis will include pH, ketones, specific gravity, bilirubin, protein, blood and glucose.

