
|                             |  |
|-----------------------------|--|
| Exclusion Criteria : | 
 
1. Subjects who have relapsed or progressed at any time prior to BMT
 
2. Subjects with known mutations that confer resistance to a BTK inhibitor.
 
3. Confirmed clinical disease progression since the time of BMT
 
4. Prior malignancy (or any other malignancy requiring active treatment), except for adequately treated basal cell or squamous cell skin cancer, in situ cervical cancer, or other cancer from which the subject has been disease free for <math>\geq 2</math> years or that will not limit survival to <math><2</math> years. The exceptions are: 
 
– Subjects treated with curative intent <math><2</math> years prior to enrollment and have a low probability of recurrence.
 
 
 
5. Clinically significant cardiovascular disease such as uncontrolled or symptomatic arrhythmias, congestive heart failure, or myocardial infarction within 6 months of screening, or any Class 3 or 4 cardiac disease as defined by the New York Heart Association Functional Classification (Appendix B).
 
6. Malabsorption syndrome, disease significantly affecting gastrointestinal function, resection of the stomach or small bowel that is likely to affect absorption, symptomatic inflammatory bowel disease, partial or complete bowel obstruction, or gastric restrictions and bariatric surgery, such as gastric bypass.
 
7. Known history of infection with human immunodeficiency virus (HIV) or any uncontrolled active systemic bacterial, fungal, parasitic or viral infection. Infections are considered controlled if appropriate therapy has been instituted and, at the time of screening, no signs of infection progression are present.
 
8. Known history of drug-specific hypersensitivity or anaphylaxis to study drug (including active product or excipient components).
 
9. Active bleeding or history of bleeding diathesis (e.g., hemophilia or von Willebrand disease).
 
10. Uncontrolled autoimmune hemolytic anemia or idiopathic thrombocytopenic purpura.
 
11. Requires treatment with a strong cytochrome P450 3A4 (CYP3A4) inhibitor/inducer (see Appendix G).
 
12. Requires or is receiving anticoagulation treatment with warfarin or equivalent vitamin K antagonists (e.g., phenprocoumon) within 7 days of first dose of study drug.
 
13. Prothrombin time (PT)/international normalized ratio (INR) or activated partial thromboplastin time (aPTT) <math>>2 \times</math> ULN (in the absence of lupus anticoagulant).
 
14. History of significant cerebrovascular disease/event, including stroke or intracranial hemorrhage, within 6 months before the first dose of study drug.
 
15. Major surgical procedure within 28 days of first dose of study drug. Note: If a subject had major surgery, they must have recovered adequately from any toxicity and/or complications from the intervention before the first dose of study drug.
 
16. Hepatitis B or C serologic status: subjects who are hepatitis B core antibody (anti-HBc) positive and who are hepatitis B surface antigen (HbsAg) negative will need to have a negative polymerase chain reaction (PCR) result. Those who are HbsAg positive or hepatitis B PCR positive will be excluded. Subjects who are hepatitis C antibody positive will need to have a negative PCR result. Those who are hepatitis C PCR positive will be excluded.
 
 |

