### **3.3 Exclusion Criteria**

Patients who meet any of the following criteria will be excluded from study entry:

1. Subjects who have relapsed or progressed at any time prior to BMT
2. Subjects with known mutations that confer resistance to a BTK inhibitor.
3. Confirmed clinical PD since the time of BMT
4. Prior malignancy (or any other malignancy requiring active treatment), except for adequately treated basal cell or squamous cell skin cancer, in situ cervical cancer, or other cancer from which the subject has been disease free for  $\geq 2$  years or that will not limit survival to  $<2$  years. The exceptions are:
  - Subjects treated with curative intent  $>2$  years prior to enrollment and have a low probability of recurrence.

5. Clinically significant cardiovascular disease such as uncontrolled or symptomatic arrhythmias, congestive heart failure, or myocardial infarction within 6 months of screening, or any Class 3 or 4 cardiac disease as defined by the New York Heart Association Functional Classification (Appendix B).
6. Malabsorption syndrome, disease significantly affecting gastrointestinal function, resection of the stomach or small bowel that is likely to affect absorption, symptomatic inflammatory bowel disease, partial or complete bowel obstruction, or gastric restrictions and bariatric surgery, such as gastric bypass.
7. Known history of infection with human immunodeficiency virus (HIV) or any uncontrolled active systemic bacterial, fungal, parasitic or viral infection. Infections are considered controlled if appropriate therapy has been instituted and, at the time of screening, no signs of infection progression are present.
8. Known history of drug-specific hypersensitivity or anaphylaxis to study drug (including active product or excipient components).
9. Active bleeding or history of bleeding diathesis (e.g., hemophilia or von Willebrand disease).
10. Uncontrolled autoimmune hemolytic anemia or idiopathic thrombocytopenic purpura.
11. Requires treatment with a strong CYP3A4 inhibitor/inducer (Appendix G).
12. Requires or is receiving anticoagulation treatment with warfarin or equivalent vitamin K antagonists (e.g., phenprocoumon) within 7 days of first dose of study drug.
13. Prothrombin time (PT)/international normalized ratio (INR) or activated partial thromboplastin time (aPTT)  $>2 \times$  ULN (in the absence of lupus anticoagulant).

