### **6.3 Baseline Study Assessments, Screening #2 Post-BMT – Day 80 to Day 100**

- Physical examination (including weight)
- ECOG performance status
- Vital signs (pulse, blood pressure, oxygen saturation, and body temperature)
- 12-lead electrocardiogram (ECG)
- Complete blood count (CBC), clinical chemistry panel, and coagulation testing
- Urinalysis
- Serum or urine pregnancy test for WoCBP
- Screening for HIV, Hepatitis B (HBV) and Hepatitis C (HCV) viruses (see Section 3.3 [exclusion criteria #7 and #17])
- Archival lymphoma biopsy collection, if not collected during Screening #1
- Blood sample collection and bone marrow aspirate for MRD analysis
- Computed tomography (CT)/ magnetic resonance imaging (MRI)/ positron emission tomography (PET) scans
- Concomitant medication review and AE evaluation

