## **7.5 Toxicity of Study Drug and Study Regimen**

### **7.5.1 Precautions and Risks Associated with Acalabrutinib**

#### **7.5.1.1 Hemorrhage**

Hemorrhagic events, including central nervous system, respiratory, and gastrointestinal hemorrhages, have been reported in clinical trials with acalabrutinib. Some of these bleeding events resulted in fatal outcomes.

The mechanism for hemorrhage is not well understood. Subjects receiving antiplatelet or anticoagulant therapies may be at increased risk of hemorrhage and should be monitored for signs of bleeding. Consider the benefit-risk of withholding acalabrutinib for at least 3 days pre- and post-surgery. Subjects with haemorrhage should be managed per institutional guidelines with supportive care and diagnostic evaluations as clinically indicated.

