## Appendix D: Schedule of Assessments

| ASSESSMENTS                                       | Screening |                       | Acalabrutinib Maintenance post-BMT a                   |              |  |   |   | End of treatment visit g | Follow-Up h |
|---|-----------|-----------------------|---|--------------|--|---|---|-------------------------------------|------------------------|
|   | Pre-BMT   | Post-BMT b | Cycle1 c
~4 mos.
Post-BMT                        |              | Cycles 2-6 d
~5-9 mos.
post-BMT | Cycles 7-12 e
~10-15 mos.
post-BMT | Cycles 13 & beyond f
≥16 mos.
post-BMT |                                     |                        |
|   |           | D1                    | D15   | D1 (±7 days) |  | D1 (±7 days)  | D1  |                                     |                        |
| Medical history & demographics         | X         |                       |   |              |  |   |   |                                     |                        |
| Physical examination & weight          | X         | X                     | X   | X            | X  | X   | X   |                                     |                        |
| ECOG PS                                    |           | X                     | X   |              | X  | X   | X   |                                     |                        |
| Vital signsi                    |           | X                     | X   |              | X  | X   | X   |                                     |                        |
| ECGj                            |           | X                     |   |              |  |   |   |                                     |                        |
| CBC & CMP                              |           | X                     | X   | X            | X  | X   | X   |                                     |                        |
| Coagulation testingu            |           | X                     |   |              |  |   |   |                                     |                        |
| Urinalysis                                 |           | X                     |   |              |  |   |   |                                     |                        |

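### Exclusion 13 depends on both PT/INR and aPTT, but the required screening panel is satisfied by either one alone

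*Combined protocol and SAP*

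**What the plan says.** Section 3.3 excludes a patient who meets any one of the listed criteria. Criterion 13 names two clotting tests, "Prothrombin time (PT)/international normalized ratio (INR) or activated partial thromboplastin time (aPTT"), with a limit of 2 × ULN for either. The Synopsis repeats it. Both versions carry the qualifier "in the absence of lupus anticoagulant".

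The content of the test is defined in two places. Section 6.5.5 reads "Coagulation testing will include PT/INR or aPTT", and footnote u of Appendix D uses the same words.

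The test is scheduled once. Section 6.3 lists "Complete blood count (CBC), clinical chemistry panel, and coagulation testing" for Screening #2 (Day 80 to Day 100 after transplant). In the Appendix D schedule, the row "Coagulation testing" has a single mark, in the post-transplant screening column. The visit lists in Sections 6.4.1 to 6.4.4 contain no coagulation test.

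**The concern.** An exclusion triggered by either of two abnormal results can be ruled out only when both results are known and acceptable. The panel definition repeats the criterion's *or*. In the criterion, that word widens the exclusion. In the panel, it halves the minimum testing. A site can therefore follow the schedule exactly and still enrol a patient who meets criterion 13, without anyone knowing.

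The criterion bears on a stated risk of the study drug. Section 7.5.1.1 reports central nervous system, respiratory and gastrointestinal hemorrhage with acalabrutinib, and adds: "Some of these bleeding events resulted in fatal outcomes". That section also says the mechanism is not well understood, and it does not link bleeding to PT or aPTT. What is at stake is therefore limited: a safety exclusion that the protocol set for itself is left unverified. No excess bleeding has been shown.

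**Working it through.** No formula applies, and the plan gives no figure to reproduce. The check compares the criterion with the test meant to support it, and then asks whether anything else in the protocol covers the difference.

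**Step 1. What the criterion needs.** There are four possible states of a patient (lupus anticoagulant absent):

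| PT/INR | aPTT | Status under criterion 13 | Detected if only PT/INR is run | Detected if only aPTT is run |
|---|---|---|---|---|
| ≤2 × ULN | ≤2 × ULN | Eligible | Not applicable | Not applicable |
| >2 × ULN | ≤2 × ULN | Excluded | Yes | **No** |
| ≤2 × ULN | >2 × ULN | Excluded | **No** | Yes |
| >2 × ULN | >2 × ULN | Excluded | Yes | Yes |

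Whichever single assay is chosen, one of the three excluded states goes undetected. Only the two-assay panel detects all three.

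**Step 2. What the schedule requires.** Section 6.5.5 and footnote u are the only current definitions of the panel, and one assay satisfies both. No other section requires the second assay.

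**Step 3. Whether a later test would reveal it.** Coagulation testing is scheduled only at Screening #2, so no later scheduled test would supply the missing result.

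**Step 4. Whether other criteria cover it.**
- Criterion 9, "Active bleeding or history of bleeding diathesis (e.g., hemophilia or von Willebrand disease"), relies on current bleeding or known history. It does not detect an unrecognised prolongation.
- Criterion 12, "Requires or is receiving anticoagulation treatment with warfarin or equivalent vitamin K antagonists", concerns one drug class. Section 5.2.2 likewise names only warfarin and equivalents, and Section 7.5.1.1 allows for subjects on antiplatelet or anticoagulant therapy.
- Criterion 14 covers cerebrovascular events in the previous 6 months.
- The laboratory limits in Section 3.2 (platelets ≥75,000/mm³, bilirubin ≤1.5 × ULN, ALT/AST ≤2.5 × ULN) include no clotting time.

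These remove some likely causes of a prolonged result, but none measures one.

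**Step 5. Size.** The minimum panel leaves 2 − 1 = 1 of the 2 named results unknown. With about 50 patients planned, the number with an unverified result is 50 × (share of patients tested with one assay only). That share is not in the documents. At 0 it gives 0 patients, and at 1 it gives 50. The range counts patients with one assay not run, not patients wrongly enrolled. The latter also depends on how often an isolated result exceeds 2 × ULN in this population, for which the documents give no basis.

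**The case against.** The strongest reply is that the criterion and the panel share the same phrase because they were meant to match: the site runs one test and excludes on that result. The summary of changes for Amendment 3.0 shows the coagulation test and its definition being added together, which fits this view. But neither text says that the assay is the site's choice. If it were, a patient with a prolonged aPTT would be eligible at one site and excluded at another, depending on which test was ordered. That reading would also need to be written down.

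A second reply is that the panel wording sets only a minimum, and Section 3.3 binds the investigator separately. Nothing permits enrolment of a patient who meets criterion 13, and an investigator may order both tests. This stands: the gap is one of detection, not of permission. It does not remove the point, because the required minimum cannot confirm the criterion and nothing prompts a site to go further.

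Third, the affected group is narrow. It needs an isolated prolongation above 2 × ULN on the untested assay alone, in a patient who passes every other bleeding-related criterion. Bleeding during treatment is also addressed in Sections 7.5.1.1, 8.1 and 8.2. This stands too, and it limits the importance of the point.

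Last, running both assays does not settle the lupus anticoagulant qualifier, since no test for it is scheduled. That is correct, but the question arises only once a prolonged result is in hand, and the second assay may be needed to show it.

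**Conclusion.** The concern holds. The required coagulation panel is not sufficient to verify exclusion 13, and no other scheduled test or criterion makes up the difference. At the minimum panel, one of the two named results is missing for each patient tested that way, which could be anywhere from none to all of about 50. The number actually enrolled in breach of the criterion cannot be estimated and is probably small. Sample size and the primary analysis of 2-year PFS are untouched. The conclusion rests on reading criterion 13 as excluding a patient abnormal on either assay, which is the natural sense of its wording under a rule that any one criterion excludes. The change is worth making because it is cheap and supports the protocol's own safety exclusion, not because harm has been demonstrated.

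**What to change.** In Section 6.5.5 and in footnote u of Appendix D, require PT/INR *and* aPTT at Screening #2. Leave criterion 13 as written. Both results are then available before the first dose. A patient with a prolonged result may still need an unscheduled lupus anticoagulant test before the qualifier can be applied.

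If the sponsor does intend one assay to be enough, criterion 13 should say so in both Section 3.3 and the Synopsis, so that the criterion and the test agree.

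The cost of the preferred change is one word in two places and one additional routine assay per patient at an existing blood draw, with no extra visit. It helps only patients still to be screened, and the documents do not say how many remain.
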